rapidly clear the antibody injected. An amount of 10 mg is expected to be adequate for tumor imaging. The rationale for 10 mg is based on the fact that this is an amount that has been used successfully with other antibodies that have minimal or minor cross reactivity with normal tissues *in vivo* (Divgi, Pandit-Taskar et al. 2007; Carrasquillo, Pandit-Taskar et al. 2011). Nonetheless, since no pharmacokinetic or imaging studies have been performed with ^{89}Zr -DFO-MSTP2109A, initial studies must determine an acceptable mass for imaging. In order to streamline antibody mass selection, initial Cohort 1A patients (up to 6 in cohort) will receive 10 mg of ^{89}Zr -DFO-MSTP2109A and will undergo pharmacokinetics and serial imaging. Decision of whether to study a second cohort, Cohort 1B, at a higher dose (20 mg) will be based predominantly on the basis of whether adequate tumor targeting is observed (tumor detection in >75% of STEAP1 positive patients). As secondary measure we will evaluate for unexpected normal organ accumulation, based on PET imaging and evidence of rapid plasma clearance based on pharmacokinetic parameters and tumor targeting. If adequate tumor targeting is achieved we will use the starting dose of 10 mg in patients enrolled in Cohort 2. The absence of antigen sink may be confirmed if pharmacokinetics show Vd of less than 3 times plasma volume, T1/2 is greater than 50 h and if visually there is no binding to normal tissues above that expected from blood pool. If there is suggestion of antigen sink, and inadequate tumor targeting, we will evaluate an additional 6 patients who will receive total dose of 20 mg (Cohort 1B). The patients in Cohort 1B also will undergo pharmacokinetics, imaging and whole body measurements as outlined for the 10 mg cohort in section 9.0. Once the milligram dose to be administered is selected, a second group of patients (Cohort 2) consisting of up to 15 patients will be enrolled, that will have only 1 whole-body scan, at a time point to be determined based on the results of Cohort 1A or 1B patients.

Because ^{89}Zr -DFO-MSTP2109A has not been evaluated in patients, toxicity assessment will be performed using Common Terminology Criteria for Adverse Events (CTCAE) v4.

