Antibody imaging will be considered feasible if 75% of the patients are antibody-imaging-positive as defined above..We will enroll 6 patients (cohort 1A) at the 10mg dose level for an initial decision on feasibility. If 4 or more of these patients have 20% or more of their active lesions detectable by ^{89}Zr -DFO-MSTP2109A then we will consider the agent feasible for imaging, otherwise we will proceed to cohort 1B. If the true feasibility rate is 40%, this rule will affords more than 82% chance that cohort 1B will be opened for enrollment; this probability is less than 17% if the true feasibility is 75%. We will also require that none of these patients experience dose severe toxicity attributable to the initial 10 mg dose before cohort 1B is opened for enrollment.

If severe adverse effect (grade 3 or 4 CTCAE) is observed in any cohort we will review with MSKCC-DSMC and IRB before continuing with accrual. If 3 patients in cohort 1A do not show acceptable imaging, as described above, we will proceed to cohort 1B.

In cohort 1B, 6 more patients will be enrolled at a higher dose (20mg) for safety and pharmacokinetic evaluation. Serial blood draws will be used to estimate the pharmacokinetic profile of the 10 and 20mg ^{89}Zr -DFO-MSTP2109A in this patient population. Pharmacokinetic analysis will be performed using a non-compartmental analysis; standard parameters such as AUC, clearance, volume of distribution, and Co will be reported. Descriptive statistics will be tabulated. If 3 patients in Cohort 1B have antibody negative imaging accrual will stop. If 4 patients in cohort 1B have positive imaging we will move to cohort 2 using the best imaging dose from cohort IA or 1B..

Based on pharmacokinetic analysis from cohorts 1A and 1B an optimal time point (based visually on optimal image quality for tumor detection and clinically/logistically feasible) will be determined for imaging and cohort 2 will enroll up to 15 patients at the dose also determined from cohorts 1A or 1B. These patients will undergo a single whole-body scan at the optimal time point. The ability of ^{89}Zr -DFO-MSTP2109A to detect tumors will be estimated from this cohort using the proportion of antibody-imaging-positive patients (within +/-22% if the true detection rate is 75%).

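### Sections 4.2 and 14.2 set different pass marks for Cohort 1A, so a result of exactly 4 of 6 is feasible under one and inadequate under the other

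*Combined protocol and SAP*

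**What the plan says.** **Section 14.2 (Primary Objective).** Six patients are enrolled at 10 mg for a first decision on feasibility. "If 4 or more of these patients have 20% or more of their active lesions detectable by" the tracer, the agent is taken as feasible; otherwise Cohort 1B follows. The rule is repeated as failures: "If 3 patients in cohort 1A do not show acceptable imaging, as described above, we will proceed to cohort 1B". Opening 1B also requires that "none of these patients experience dose severe toxicity attributable to the initial 10 mg dose before cohort 1B is opened for enrollment". At a true rate of 40% the chance of opening 1B is given as more than 82%, and at the target rate "this probability is less than 17% if the true feasibility is 75"%. The same section also states a general criterion: "Antibody imaging will be considered feasible if 75% of the patients are antibody-imaging-positive as defined above".

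**Section 4.2 (Design).** The decision on a 20 mg cohort "will be based predominantly on the basis of whether adequate tumor targeting is observed (tumor detection in >75% of STEAP1 positive patients"). Unexpected organ uptake and rapid plasma clearance are secondary measures. Two consequences follow: "If adequate tumor targeting is achieved we will use the starting dose of 10 mg in patients enrolled in Cohort 2"; and "If there is suggestion of antigen sink, and inadequate tumor targeting, we will evaluate an additional 6 patients" at 20 mg.

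**Elsewhere.**
- The Schema in section 1.0 makes Cohort 1B depend on suboptimal imaging or pharmacokinetics.
- Section 9.3 counts a patient as positive if any active lesion is seen.
- Section 12.0 defines successful imaging as detection in at least 75% of STEAP1-positive patients.

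**The concern.** Both sections govern one decision: carry 10 mg into Cohort 2, or first enroll six more patients at 20 mg. Four positives and two negatives is a pass in 14.2, whether counted as successes or as failures. The same result is 66.7% detection, short of the mark in 4.2. There is no precedence clause.

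The difference is hard to dismiss as a true rate set beside a sample pass mark, because 4.2 speaks of what is observed.

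If the result is 4 of 6, either course could be defended after the data are seen, which a prespecified rule is meant to prevent. At stake are six further patients, each with up to four PET/CT scans, serial blood sampling and, on Table 3's mouse-based estimate, a total effective dose of about 9.6 rem.

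**Working it through.** **Inputs.** n = 6 in Cohort 1A (14.2). Pass marks: at least 4 of 6 (14.2) and more than 75% (4.2). True rates 40% and 75% (14.2). STEAP1 positivity is an eligibility condition (6.2 and 14.2), so all six patients belong in the 4.2 denominator.

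**Assumptions.** All six patients are evaluable, and both sections count the same per-patient endpoint.

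**Step 1: reproduce the plan's figures.** Let X be the number of imaging-positive patients, X ~ Binomial(6, p). Under 14.2 the imaging count points to 1B when X ≤ 3.
- p = 0.40: P(X ≤ 3) = 0.8208. Stated: more than 82%.
- p = 0.75: P(X ≤ 3) = 0.1694. Stated: less than 17%.

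Both agree.

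**Step 2: convert the 4.2 mark to a count.** 0.75 × 6 = 4.5, so more than 75% needs at least 5 of 6 (83.3%). 4/6 = 66.7% falls short.

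**Step 3: compare the sections by outcome.**

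| Positives | 14.2 | 4.2 adequacy | 4.2 action |
|---|---|---|---|
| 5 or 6 | feasible at 10 mg | adequate | keep 10 mg |
| 4 | feasible at 10 mg | inadequate | 1B if a sink is suspected; otherwise none stated |
| 3 or fewer | open 1B | inadequate | 1B if a sink is suspected; otherwise none stated |

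Only 4 of 6 gives conflicting adequacy verdicts. At 3 or fewer without a sink, 14.2 is explicit and 4.2 is silent.

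**Step 4: chance of the disputed result.** P(X = 4) = 15 p⁴(1 − p)².

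| True rate p | 0.40 | 0.50 | 0.60 | 2/3 | 0.75 | 0.80 | 0.90 |
|---|---|---|---|---|---|---|---|
| P(X = 4) | 0.138 | 0.234 | 0.311 | 0.329 | 0.297 | 0.246 | 0.098 |

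The maximum is at p = 2/3.

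**Step 5: a pure 5-of-6 rule.** P(X ≤ 4) = P(X ≤ 3) + P(X = 4).
- p = 0.40: 0.8208 + 0.1382 = 0.9590.
- p = 0.75: 0.1694 + 0.2966 = 0.4661 from unrounded terms.

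**Step 6: the two assumptions.**
- Section 4.2 says up to six patients. With five evaluable, 4/5 = 80% would meet its mark and the conflict at four positives disappears.
- Section 4.2 does not define detection in a patient. The any-lesion rule in 9.3 and the 20% rule in 14.2 coincide up to five active lesions (1/5 = 20%) and can differ from six upward (1/6 = 16.7%).

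**The case against.** The strongest reply is that 14.2 is the operating rule. It gives a count, restates it as failures, attaches probabilities, and calls the step an initial decision. Its 75% criterion stands beside the 4-of-6 count, which suggests a target rate with a looser small-sample screen. Section 4.2 is then only a design overview. This is plausible and is probably how the trial would be run. It does not settle the matter: 4.2 refers to observed detection, and nothing gives 14.2 precedence.

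A second reply concerns how far 4.2 goes, and it stands. A reader might infer that 4.2 keeps 10 mg only if the 75% mark is exceeded, and so orders Cohort 1B at 4 of 6. The text does not say that. The mark is the predominant basis, and meeting it is stated as sufficient for 10 mg, not as necessary. The one sentence in 4.2 that opens 1B joins a suspected antigen sink to inadequate targeting, and 4.2 expects no sink. At 4 of 6 without a sink, 4.2 neither confirms 10 mg by its adequacy route nor opens 1B.

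Nor are the 82% and 17% in error: 14.2 ties them to its own rule, and they reproduce. Section 14.2 is not silent on a sink either; it keeps the same 20% definition of a positive patient when one is present, so a sink does not alter its count.

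Finally, the consequence is bounded. The 20 mg cohort is already provided for, 14.2 lets the better dose go forward if 1B passes, and the Cohort 2 estimate is not invalidated.

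**Conclusion.** The thresholds in 4.2 and 14.2 disagree, and the plan should be corrected before a 4-of-6 result can occur. With six evaluable patients and a common per-patient endpoint, that result has probability 29.7% at a true rate of 75% and 13.8% at 40%. Between 40% and 90% it ranges from 9.8% (at 90%) to 32.9% (at two thirds).

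These are chances of conflicting adequacy verdicts. A reader might take 29.7% as the chance of contradictory instructions, but it is only an upper bound on that: an explicit contradiction also needs a suspected antigen sink, whose probability the documents do not give. Likewise, 95.9% and 46.6% describe a pure 5-of-6 rule that no section states in full; the joint condition in 4.2 would open 1B less often.

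The role of a sink and the per-patient definition are unclear across sections. They are secondary to the threshold.

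**What to change.** Make the 14.2 count the single rule: at least 4 of 6 patients with 20% or more of active lesions detectable.

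- **4.2:** replace the 75% mark with that count and cross-refer to 14.2, including its toxicity condition.
- **4.2 and the Schema:** state whether a suspected antigen sink is required, sufficient or only supportive for opening 1B, and use the same wording in both.
- **9.3:** state that the 20% definition in 14.2 is the one counted for the decision, not the any-lesion definition.
- **14.2 and 12.0:** label the 75% figures as the target rate, not the six-patient pass mark.

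If 5 of 6 is intended, change the Cohort 1A counts in 14.2 to five positives and two negatives, and restate the probabilities as 95.9% and 46.6%. Also state whether Cohort 1B's rule of four positives or three negatives changes to match; otherwise the two doses have different pass marks.

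The cost is amendment wording. Keeping 4 of 6 adds no patients and leaves the stated probabilities and the toxicity condition unchanged. Moving to 5 of 6 would make enrollment of the six 20 mg patients more likely.

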14.1 BIOSTATISTICS

14.2 Primary Objective

The primary objective of this protocol is to determine the feasibility, safety and tolerability of single dose administration of ^{89}Zr -DFO-MSTP2109A antibody.

A patient with STEAP1 positive tumor will be considered antibody-imaging-positive if 20% or more of the active lesions are detectable (STEAP1 positivity is an eligibility criterion for protocol 11-016 which forms the basis of eligibility for this protocol; see section 6 for details). Active lesion means any lesion that was identified by conventional imaging methods and clinical data at baseline. We have selected a low threshold of 20% for this first imaging study for 3 reasons: 1) we do not know what the heterogeneity of antigen expression is within a number of lesions in the same patient; 2) we will consider positive any lesion based on conventional clinical imaging criteria, in which case some lesions considered positive may be false positive and more importantly 3) our main emphasis is to evaluate whether patients whose tumor images are positive with ^{89}Zr -DFO-MSTP2109A are more likely to have a response to the antibody based drug conjugate used under

MEMORIAL SLOAN-KETTERING CANCER CENTER IRB PROTOCOL

IRB#:12-178 A(3)

protocol 11-016. Thus, we do not want to discard this agent if we can use it as a **theranostic** (defined as an agent that is integrated into the drug development process so as to guide patient selection and drug development) for the development of the antibody base drug conjugate being used under protocol 11-016. Nonethe less, we intend to evaluate treatment response of all available lesions in this way we will maximize our ability to determine the relationship between uptake of antibody and response.

If, for any patient, there is evidence of an “antigen sink” based on rapid clearance < 50 h or $Vd > 3$ times plasma volume, we will consider a patient antibody-imaging-positive if 20% or more of the active lesions are visualized. The presence of an “antigen sink” may bind a significant amount of antibody and make less available for binding to tumor.

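### Sections 14.2 and 4.2 set different bars for keeping 10 mg or opening the 20 mg cohort (4 of 6 against more than 75%), and the stated 82% and 17% fit only the first

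*Combined protocol and SAP*

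**What the plan says.** Section 14.2 enrolls six patients at 10 mg (cohort 1A) and sets a numerical gate: "If 4 or more of these patients have 20% or more of their active lesions detectable by" the labeled antibody, "then we will consider the agent feasible for imaging, otherwise we will proceed to cohort 1B". It restates the gate as three unacceptable results in 1A leading to 1B, and gives its properties: "If the true feasibility rate is 40%, this rule will affords more than 82% chance that cohort 1B will be opened for enrollment", and under 17% if the true rate is 75%. Opening 1B also requires that "none of these patients experience dose severe toxicity attributable to the initial 10 mg dose before cohort 1B is opened for enrollment". In 1B the same count applies: "If 3 patients in Cohort 1B have antibody negative imaging accrual will stop", while four positives lead to cohort 2. A sink does not enter the gate. Where one is suspected, section 14.2 repeats the ordinary definition: "we will consider a patient antibody-imaging-positive if 20% or more of the active lesions are visualized".

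Section 4.2 says that the decision on a second cohort depends predominantly on "whether adequate tumor targeting is observed (tumor detection in >75% of STEAP1 positive patients"; normal-organ uptake and plasma clearance are a secondary measure. If targeting is adequate, 10 mg goes to cohort 2. The sentence that actually opens 1B reads: "If there is suggestion of antigen sink, and inadequate tumor targeting, we will evaluate an additional 6 patients", at 20 mg. The same section expects no sink.

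The schema in section 1.0 gives a third form, in which either poor images or poor kinetics is a reason for 1B. A 75% bar for success also appears in section 12.0 and in 14.2 itself.

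**The concern.** This is the trial's main adaptive decision, and two sections answer it differently. With 4 of 6 positive, a team working from 14.2 takes 10 mg to cohort 2. A team working from 4.2 finds 10 mg inadequate and, if it lets targeting decide, enrolls up to six more patients at 20 mg. Cohort 2, up to 15 patients, supplies the estimate of detection ability, so the section followed can change the mass at which that estimate is made.

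The published chances of opening 1B describe only one of the two rules. The sink wording adds a further doubt: applied literally, the 4.2 sentence would not open 20 mg after 10 mg had failed on imaging unless a sink was also suspected.

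**Working it through.** **Inputs.** Cohort size 6 and true rates of 40% and 75% are from section 14.2. The 60% rate is an added intermediate value. The 14.2 gate is 4 or more positive. The 4.2 gate is more than 0.75 × 6 = 4.5, so 5 or more. X is the number of positive patients in 1A, taken as binomial: P(X = k) = C(6,k) p^k (1 − p)^(6 − k). The toxicity condition is taken as met.

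**Step 1: the plan's own figures (4 of 6).** P(open 1B) = 1 − P(X ≥ 4).
- p = 0.40: 1 − (0.1382 + 0.0369 + 0.0041) = 0.8208, against a stated value above 82%.
- p = 0.75: 1 − (0.2966 + 0.3560 + 0.1780) = 0.1694, against a stated value below 17%.

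Both reproduce.

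**Step 2: the 4.2 bar alone (5 of 6).** P(open 1B) = 1 − P(X ≥ 5).
- p = 0.40: 1 − 0.0410 = 0.9590.
- p = 0.75: 1 − 0.5339 = 0.4661.

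Neither matches the stated figures. Requiring a sink as well does not rescue the match. If a sink is declared with probability s, unrelated to imaging, P(open 1B) becomes s × 0.9590 and s × 0.4661. Matching the stated values needs s = 0.8208/0.9590 = 0.86 at 40% and s = 0.1694/0.4661 = 0.36 at 75%. No single s fits both.

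**Step 3: where the two bars part.** They differ only at X = 4, with probability 15 p^4 (1 − p)^2.
- p = 0.75: 29.7%.
- p = 0.60: 31.1%.
- p = 0.40: 13.8%.

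**Step 4: the sink sentence taken literally, with no sink found.** 14.2 opens 1B at X ≤ 3 and the 4.2 sentence does not. P(X ≤ 3) is:
- p = 0.75: 16.9%.
- p = 0.60: 45.6%.
- p = 0.40: 82.1%.

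Steps 3 and 4 belong to different readings of section 4.2: targeting alone decides in step 3, while a sink is also required in step 4.

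**The case against.** The strongest defence is that section 14.2 is the statistical section, its rule is clear and its arithmetic is right, so a sensible team would follow it. The arithmetic does stand; a reader who inferred that 82% and 17% are errors would be mistaken. But nothing in the text gives 14.2 precedence. The 75% in section 4.2 also cannot be set aside as a final success bar, because that section ties it expressly to the decision on a second cohort. Section 14.2's own 75% feasibility criterion adds to the doubt, since 4 of 6 is 66.7%.

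The defence is stronger on the sink. A reader might infer that section 4.2 forbids 20 mg unless a sink is found. The documents do not support that. The sentence says when 1B will open, not that it opens only then; the same section makes targeting predominant and kinetics secondary; and the schema uses *or*. The sink wording is inconsistent, but it is not a firm contrary rule.

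A reader might also add steps 3 and 4 and claim disagreement in 29.7% + 16.9% = 46.6% of trials at a true 75%. That mixes the two readings. If a sink is required and none is found, neither section opens 1B at 4 of 6; section 4.2 then merely leaves a gap. Finally, a reader might look for a missing tie-break between masses, or a stop in 1B after 10 mg had passed. Neither can arise under 14.2 alone, because 1B then opens only after 10 mg has failed.

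**Conclusion.** The inconsistency is real and should be corrected. The thresholds conflict at exactly 4 of 6, which happens in about 30% of trials at the plan's favourable rate and about 14% at its unfavourable rate. The stated probabilities of opening 1B hold only under 4 of 6. The role of the sink is unsettled across sections 1.0, 4.2 and 14.2; the step 4 figures apply only if the *and* sentence is enforced literally and no sink appears.

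These sizes assume six evaluated patients, independent results with a common positivity rate, and one definition of a positive patient. The documents give no probability of a sink, so no combined figure is claimed.

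**What to change.** Make section 14.2 the single rule and have sections 1.0 and 4.2 refer to it. In section 4.2, replace the more-than-75% bar with 4 or more of 6, using the definition of 20% of active lesions (section 9.3 counts any active lesion). Report sink and pharmacokinetic findings descriptively, not as a required trigger. State the rule as:

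- 1A with 4 or more of 6 positive: cohort 2 at 10 mg.
- Third negative in 1A (so at most 3 of 6 positive), and no severe toxicity attributable to 10 mg: open 1B at 20 mg.
- 1B with 4 or more of 6 positive: cohort 2 at 20 mg.
- Third negative in 1B: stop.

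Keep the existing DSMC and IRB review of any grade 3 or 4 event throughout. Add a sentence saying that the 75% bar in sections 12.0 and 14.2 is the target for the final detection estimate and that 4 of 6 is the interim gate.

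If the sponsor prefers 5 of 6, restate P(open 1B) as 0.959 at a true 40% and 0.466 at 75%, and apply the same bar in 1B. At a true 75% that adds at most 6 × 0.2966 = 1.8 patients on average in 1B.

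The default costs a short amendment and adds no patients. What is given up is any power of pharmacokinetics to decide whether 1B opens.

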9.1 TREATMENT/INTERVENTION PLAN

9.2 Pharmacokinetics

Patients are not required to fast before ⁸⁹Zr-DFO-MSTP2109A injection or imaging.

Catheter insertion and Pharmacokinetics

If feasible, 2 intravenous catheters (Hep-Lock) will be placed by staff in the Nuclear Medicine department for radiopharmaceutical administration and blood sampling, or alternatively a central line may be used for injection or sampling. The intravenous catheter will be removed at the conclusion of the imaging session. If two lines are not feasible, one line will be used for both injection and PK sampling with intervening 10 cc saline flush and change of catheter hub. Patients in Cohort 2 (no pharmacokinetics, will not require a second catheter).

⁸⁹Zr-DFO-MSTP2109A: To determine clearance and for metabolite analysis of the drug, Cohort 1A and 1B patients (up to 6 patients per cohort) receiving ⁸⁹Zr-DFO-MSTP2109A will have serial blood samples drawn. Blood samples will be obtained in green top tube:

- Just prior to injection of ⁸⁹Zr-DFO-MSTP2109A (baseline)
- Approximately 5 ± 2, 15 ± 5, 30 ± 9, 60 ± 19, and 120 to 240 minutes after injection of the tracer.
- One sample at the time of each subsequent day of imaging (24 ± 8h, ~48-96h and ~120-168h post injection).

These data are used to determine the time-activity curves for plasma (% injected dose/liter). Blood is centrifuged, and the plasma pipetted and counted. Samples may be tested for breakdown products by TCA or HPLC. Blood will also be aliquoted for sampling, if in the first 3 patients no binding is observed to blood elements only plasma sampling will be counted in subsequent patients.

For each blood sample, 4-6 mL of blood will be drawn in green top tubes.

Patients in Cohort 2 will undergo injection and 1 imaging session, but no pharmacokinetics will be performed.

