Images will be analyzed with ROI and SUVmean and max measurements will be obtained. The serial quantitative data obtained over the various organs of interest (heart, liver, spleen, kidney, lung and any other organ that exhibits uptake will be collected. These data can then be utilized to determine organ time activity curves and the dosimetry can be calculated. Uptake and clearance values will be summarized using descriptive statistics (mean, median standard deviation. Once the biodistribution and pharmacokinetics have been characterized, subsequent patients will not require serial imaging and pharmacokinetics, but rather will have a single scan at an optimal time point determined based on the patients in cohort 1A and or cohort 1B. We will determine the time at which the greatest number of lesions are seen. This is likely to be between 3-8 days, but choice will be based on the first Cohort 1 patients' data, using the most frequent day at which the most lesions are seen and/or at times at which best contrast is observed determined visually. Thus, for the remainder of the patients in Cohort 2, PET scan will be performed once. The timing of this scan will be determined based on findings from Cohort 1A and/or 1B, as described above.

Infusion reactions with MSTP2109A intact IgG have not been evaluated. Infusion reaction to the ADC DSTP3086S antibody drug conjugate in 18 patient treated thus far have been minor and not clinically significant (i.e. none or Gr1). In the event of fever, rigors, shortness of breath, or other evidence of infusion reaction, patients may receive diphenhydramine 25-50 mg IV and Tylenol 650 mg PO as felt to be clinically appropriate by the treating physician. The emission data are typically acquired for 3–10 minutes per bed position depending upon the time post-injection and visual quality of the images. Index lesions will be identified based on the patient's conventional diagnostic imaging.

Images will be stored as Digital Imaging and Communications in Medicine (DICOM) on the PACS and HERMES. Images to be sent out to Genentech will be burned on a CD or equivalent by patient. All images will be anonymized according to institutional policy with the patients code used as identifiers.

No decision on the patients' health care management will be made on the basis of Imaging with ⁸⁹Zr-DFO-MSTP2109A.

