9.4 Whole body probe measurements (Cohort 1)

Patients in Cohort 1 will undergo whole body dose measurement using a NaI probe placed at ~3 meters from the patient. These measurements will be performed the day of injection of ⁸⁹Zr-DFO-MSTP2109A before voiding and after first void, and at each time the patient returns for imaging (typically less than 5 minutes).

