Normal-organ radiation absorbed doses and the effective dose for ^{89}Zr -DFO-MSTP2109A in human were estimated based on measured time-activity data in mice. The time-activity data (percent of the injected dose per gram (%ID/gm) versus time (t) post-administration) for each organ were fit to an exponential functions and the resulting function were analytically integrated (incorporating the radioactive decay of ^{89}Zr) to yield the residence time (cumulated activity) of ^{89}Zr in each organ. The mouse organ ^{89}Zr residence times were converted to ^{89}Zr residence times in human organs (for the 70-kg Standard Man anatomic model) by adjusting for the difference in fractional organ masses between mice and humans. The resulting human residence times were then entered into the OLINDA/EXM radionuclide dosimetry program, which implements the MIRD (Medical Internal Radionuclide Dosimetry) algorithm, to yield the normal-organ radiation absorbed doses (in rad) and effective dose (in rem) for ^{89}Zr -DFO-MSTP2109A in man. Assuming a 5-mCi administered activity of ^{89}Zr -DFO-MSTP2109A and a low-dose (80 mA) and three very-low-dose (10-mA) CT scans are to be performed, with approximate CT effective doses of 0.90 rem and 0.11 rem the radiation dosimetry is tabulated below.

Table 3. ^{89}Zr -DFO-MSTP2109A Absorbed Doses in 70-kg Standard Man per MIRD (OLINDA) Formalism Based on Biodistribution Data in Mice¹

^{89}Zr -DFO-MSTP2109A AP Antibody Radiation Doses in the 70-kg Standard Man

^{89}Zr Administered Activity:	5	mCi
# of 80-mA CT scans:	1	
Organ dose per 80-mA CT scan:	0.90	rem
# of 10-mA CT scans:	3	
Organ dose per 10-mA CT scan:	0.10	rem
Total CT organ dose:	1.20	rem

	Absorbed Doses		
	^{89}Zr -DFO-MSTP2	P2109A	
		rad/5	rad/mCi
Adrenals	1.56	7.80	9.00
Brain	0.68	3.42	4.62
Gallbladder Wall	1.32	6.60	7.80
LLI Wall	1.52	7.60	8.80
Small Intestine	1.25	6.25	7.45
Stomach Wall	1.39	6.95	8.15
ULI Wall	1.34	6.70	7.90
Heart Wall	1.50	7.50	8.70
Kidneys	2.33	11.7	12.9
Liver	1.81	9.05	10.25
Lungs	2.82	14.10	15.30

MEMORIAL SLOAN-KETTERING CANCER CENTER
IRB PROTOCOL

IRB#:12-178 A(3)

Muscle	1.21	6.05	7.25
Pancreas	1.42	7.10	8.30
Red Marrow	3.26	16.3	17.5
Osteogenic Cells	4.59	23.0	24.2
Skin	0.71	3.55	4.75
Spleen	1.98	9.90	11.10
Testes	0.82	4.09	5.29
Thymus	1.11	5.55	6.75
Thyroid	1.03	5.15	6.35
Urinary Bladder Wall	1.04	5.20	6.40
Total Body	1.31	6.55	7.75
Effective Dose Equivalent	1.87	9.35	10.55
Effective Dose	1.68	8.40	9.60

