This study does not intend to find the maximal tolerated dose of DFO-MSTP2109A. This is a diagnostic agent that is expected to have low incidence of adverse events. Patients will be monitored closely looking for evidence of adverse events. Because patients will likely start new therapies within 2 weeks of receiving ^{89}Zr -DFO-MSTP2109A only short term toxicity will be evaluated. The safety and tolerability of ^{89}Zr -DFO-MSTP2109A will be assessed using the following primary safety outcome measures: Incidence and nature of incidence, nature, and severity of adverse events; and change in vital signs and clinical laboratory results. Incidence and

MEMORIAL SLOAN-KETTERING CANCER CENTER IRB PROTOCOL

IRB#:12-178 A(3)

severity of adverse events will be summarized with descriptive statistics.

Dosimetry: SUVmax/mean (that can easily be converted to %ID/g) in normal organs of patients from Cohort 1A and Cohort 1B will be determined and this data over time will be used to determine the residence time in each visualized organ (liver, spleen, kidney and lung), other organ will be evaluated if clinically appropriate. The median residence time value will be used in OLINDA software to calculate the dosimetry.

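### Dosimetry plan: one median residence time per organ goes into OLINDA, with no per-patient dose, no between-patient spread and no split between the 10 mg and 20 mg cohorts

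*Combined protocol and SAP*

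**What the plan says.** Dosimetry from human biodistribution data is a secondary objective (section 2.2). The method is in the Dosimetry paragraph at the end of section 14.2:

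- Input: "SUVmax/mean (that can easily be converted to %ID/g) in normal organs of patients from Cohort 1A and Cohort 1B will be determined".
- Source organs: "residence time in each visualized organ (liver, spleen, kidney and lung), other organ will be evaluated if clinically appropriate".
- Summary: "The median residence time value will be used in OLINDA software to calculate the dosimetry".

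Section 9.3 covers the same measurements in different terms. It says "SUVmean and max measurements will be obtained", and its organ list is wider: "heart, liver, spleen, kidney, lung and any other organ that exhibits uptake will be collected". It plans mean, median and standard deviation for uptake and clearance, but not for absorbed dose.

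Two other data streams are collected in Cohort 1. Section 9.2 says of the blood samples: "These data are used to determine the time-activity curves for plasma". Section 9.4 says Cohort 1 patients "will undergo whole body dose measurement using a NaI probe". Neither section, nor 14.2, says how these data enter the dose calculation.

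Cohort 1A has up to 6 patients at 10 mg. Cohort 1B, if opened, has 6 at 20 mg (sections 4.2 and 14.2).

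**The concern.** Taking the median organ by organ before the dose calculation discards the patient as the unit of analysis. The values entered for liver, spleen, kidney and lung may each come from a different man, so together they need not be consistent with anyone's whole-body activity. The output is a single dose per organ, and nothing in the plan conveys how far patients differ around it.

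Section 14.2 also draws on both mass cohorts without saying whether they are kept apart. Section 4.2 ties Cohort 1B to a suspected antigen sink with inadequate tumor targeting. Kinetics could then plausibly depend on mass, yet Cohort 2 receives only one of the two masses.

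Three details that determine the result are left open: which SUV measure gives residence time, how red marrow and the remainder of the body are obtained, and which organ list applies. The human estimate is worth getting right because the only existing one, Table 3 in section 11.0, is scaled from mice, and section 3.2.2 reports that the antibody does not bind the mouse orthologue of the target.

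**Working it through.** **1. Reproduce Table 3 (section 11.0).** Inputs: rad/mCi from the table, 5 mCi, and a CT contribution of 0.90 + 3 × 0.10 = 1.20. Formula: total = rad/mCi × 5 + 1.20.

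| Tissue | rad/mCi | × 5 | + 1.20 | Table 3 |
|---|---|---|---|---|
| "Osteogenic Cells" | 4.59 | 22.95 | 24.15 | 24.2 |
| Red marrow | 3.26 | 16.30 | 17.50 | 17.5 |
| Lungs | 2.82 | 14.10 | 15.30 | 15.30 |
| Kidneys | 2.33 | 11.65 | 12.85 | 12.9 |
| Spleen | 1.98 | 9.90 | 11.10 | 11.10 |
| Liver | 1.81 | 9.05 | 10.25 | 10.25 |

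All rows of the table reproduce to within 0.05. On the tracer component alone, osteogenic cells are 4.59 / 2.82 = 1.63 times, and red marrow 3.26 / 2.82 = 1.16 times, the highest of the four organs named in 14.2. Neither is named as a source region in 9.3 or 14.2. (The text above Table 3 gives 0.11 rem per low-current CT, which would total 0.90 + 3 × 0.11 = 1.23. This does not touch residence times.)

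**2. What a median input does.** Under the MIRD formalism that OLINDA implements, the dose to a target is linear in the residence times: D(target) = Σ over sources of τ(source) × S(target ← source). With one fixed anatomic model, entering mean residence times returns exactly the mean of the patients' doses, because means add. Medians do not add: Σ median(τ) is in general not median(Σ τ). A dose built from organ-wise medians is therefore generally neither the mean nor the median of the patients' doses.

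**3. What pooling by mass does.** With six patients at each mass, the pooled median lies between the 6th and 7th ordered values. If an organ's residence times at the two masses did not overlap, those two values would be the top of the lower group and the bottom of the upper group, so the pooled median would describe neither mass. This arises only if Cohort 1B opens. Section 14.2 puts that chance below 17% if the true feasibility rate is 75% and above 82% if it is 40%.

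**4. What is not shown.** The documents give no human residence times or between-patient variation. Simulation with lognormal residence times and an assumed between-patient CV of 20–50% gives:

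| Patients | Mean of sample median / true mean | Relative SE of median | Highest patient / mean |
|---|---|---|---|
| 6 | 0.986 to 0.925 | 9% to 22% | 1.27 to 1.71 |
| 12 | 0.983 to 0.908 | 7% to 16% | 1.36 to 2.01 |

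**5. SUV measure.** Residence time is integrated total organ activity, so it needs mean concentration times organ mass. If SUVmax were used instead, the excess would be about 11% (50 voxels, voxel CV 5%) to 65% (1000 voxels, voxel CV 20%). Voxel counts and CVs are assumptions, with voxels taken as independent and normal.

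**The case against.** A reader might infer that only four organs will be assessed. The text does not support that: 14.2 allows others where clinically appropriate, and 9.3 adds the heart and any organ showing uptake. The list also concerns where activity is measured, not which tissues receive a reported dose. Section 11.0 describes OLINDA turning residence times into doses for many tissues, and Table 3 includes marrow and osteogenic cells. The open question is how the marrow input is obtained.

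A reader might also infer that the estimate is probably biased, or that activity outside the named organs is lost. Neither is shown. Both SUV measures are collected and nothing says SUVmax drives residence time. SUVmax would push upward, the median of skewed values slightly downward, and the direction for marrow is unknown. No section excludes the remainder of the body; the probe data exist and their use is simply unstated. Nor do the documents say that the human result will replace the mouse projection in Table 3.

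A median is a stated, reproducible and robust summary for 6 to 12 patients, and spread of uptake and clearance is already planned. No mass choice, stopping rule or sample size depends on dosimetry.

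These replies stand. They do not answer the remaining point: spread of uptake is not spread of absorbed dose, organ-wise medians do not describe a patient, and the two masses are not separated.

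**Conclusion.** The point holds as a low-priority improvement to a descriptive secondary objective. As written, the plan yields one dose per organ with no per-patient values, no spread and no stated split by mass, from inputs that need not fit any patient's whole-body activity. That follows from the text and the linearity of the dose calculation, without numerical assumptions.

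The size does rest on assumptions. With a between-patient CV of 20–50%, the unreported highest patient would average roughly 1.3 to 2.0 times the mean, and the median would sit about 1–9% below it. The 11–65% figure for SUVmax applies only if that measure were chosen, which the documents do not say. The Table 3 ranking is a mouse projection; it is a reason to specify a marrow method, not evidence of what human doses will be. No primary conclusion, decision rule or sample size changes.

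**What to change.** Amend the Dosimetry paragraph of 14.2 as follows:

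- Run OLINDA for each Cohort 1 patient. Report mean or median, SD and range of organ and effective doses, separately for 10 mg and 20 mg. With 6 patients the observed range also serves as a distribution-free interval for the population median, with coverage 1 − 2 × (1/2)⁶ = 96.9%.
- State that residence time comes from SUVmean times organ mass; keep SUVmax for description only.
- State that the blood/plasma curve is used for red marrow and the whole-body probe counts for the remainder of the body.
- Use one source-organ list in 9.3 and 14.2.

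The cost is a few lines of text and some extra analyst time. The activity data are already scheduled, so no patient procedure is added.
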